### **Rationale for Marijuana Administration Procedure.**

With respect to the naturalistic aspects of the design, it is important to note that we carefully considered alternative designs. For example, we previously conducted a study that involved a highly controlled laboratory administration of marijuana obtained from the NIDA supplier in Mississippi (Schacht, Selling, & [name], 2009). As noted previously, the external validity of the study was compromised because the marijuana was of significantly poorer quality than subjects had ever experienced. Further, laboratory protocols are unlikely to mirror real-world marijuana use. Thus, those procedures simply did not, and cannot reflect the strains of marijuana and methods of administration of marijuana in states like Colorado. Because the long-term goal of this work is to better understand the effect of different levels of cannabinoids that result from marijuana use in order to develop more effective harm reduction strategies, we decided that it was more important to emphasize external validity. The disadvantage of our design is that we have little control over how the participants use the marijuana or how much they use. To address this limitation, both in our pilot study and in this application, we rely on blood quantitation of cannabinoids to determine the level of THC and CBD in each subject in both Study 1 and Study 2. Thus, regardless of how the participant uses the marijuana, we have an objective measure of the dose received for both THC and CBD for each subject, which is the sine qua non of pharmacological research. This aspect is also critical for our analysis approach, which emphasizes the analysis of blood levels of THC and CBD in Study 2 as continuous measures. In this way, we also capitalize on the greater variability in blood levels expected in the observational design by analyzing overall levels of THC and/or CBD as well as the ratio of THC to CBD (in Study 2).

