### **Marijuana Administration at Home.**

Unlike other studies done in the United States to date, the proposed work will utilize a design that is observational but contains some experimental elements. Specifically, at the end of Appointment 1 (Baseline/Session 1) participants will be given instructions to purchase 3 grams of either a normally high THC strain, a medium THC strain, or a low THC strain at a dispensary (The Farm) in Boulder, Colorado. The normally high THC smoked flower strain contains 18% THC and 0% CBD and edibles can range from a low of 2.5 mg to greater than 10 mg of THC and 0 mg of CBD. **Please note the term “high” is relative given that the average potency in Colorado exceeds 18% and edibles are normally packaged in 10 mg THC doses.** The medium flower strain contains 12% THC and 0% CBD. The low flower THC strain contains 6% THC and 0% CBD. Colorado requires all strains of flower and edibles to be tested by a state licensed lab, which allows us to have a precise measure of potency to operationalize our high, medium, and low THC strains. Furthermore, the dispensary that we will work with (The Farm - see letter of support) performs cannabinoid and terpene potency testing on each batch produced. The dispensary will set aside a specific lot of the strains which will be labeled as “Strain A”, “Strain B”, and “Strain C” such that participants, dispensary staff, and research staff will be blind to which strain was purchased. Thus, 3 grams of each marijuana strain will be packaged in childproof bottles labeled as “Strain A”, “Strain B”, and “Strain C.” Our preliminary data suggests that 3 grams is sufficient for the study. [name] (co-investigator) will maintain the blind. The instruction to purchase “A” or

“B” or “C” will be urn randomized across participants such that equal numbers of male and female participants are included in the high, medium, and low conditions. The observational aspect of the design involves the instruction that participants can use as little or as much of the marijuana as they wish during the five days prior to the experimental appointment. The five-day period allows each participant to become accustomed to the strain. Subjects are prompted by email or text message to report how much was used each day using an online reporting system. On the fifth day, the research assistant calls the participant one hour prior to their appointment to remind the participant about the upcoming appointment from the research team.

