### **Power Analysis and Sample Size Requirement for Hypotheses 1 and 2**

Sample size was selected to permit analysis of the primary research questions at two-tailed alpha of .05 and power level of .80. Estimates of effect size follow Cohen (1988) and were conducted in G\*Power 3 (Faul et al., 2007). The primary analysis is the test of the strain X time interaction effects across repeated assessments of THC in the blood as well as assessments of working memory and the rewarding effects of the marijuana. To be conservative, we thus estimated an ICC of .60. Using a mixed model ANOVA design, with three groups, four assessment points, and an average ICC = .6 between assessment points, a total n=99 (33 per group) will allow us to detect an interaction effect as small as  $f=.12$ .

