### **The impact of attrition.**

It is anticipated that some attrition will occur in this population. Based on our current pilot study and previous marijuana studies, we anticipate a 10% attrition rate between Appointment 1 baseline session and Appointment 2 the experimental session, though we have not experienced and do not anticipate differential attrition by condition. Thus, to allow for attrition, we assume a 90% retention rate over the course of data collection. To adjust for this attrition rate, we will recruit  $n\approx 111$  participants ( $n=37$  per group). Our approach to power analysis and accounting for attrition is extremely conservative, in that the techniques we will utilize in data analysis use state of the art recommendations in iterating the estimation of missing data (Schafer & Graham, 2002; Little, 1988). All analyses are intent-to-treat and all available data are utilized in analyses.

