**Hypothesis 2** tests whether blood levels of THC are positively associated with diminished working memory and greater rewarding effects of the marijuana, operationalized with the DEQ. If analyses of Hypothesis 1 show that there are main effects by group suggesting that the higher THC strain results in significantly higher THC levels in the blood than the medium or low THC strains, the between-groups variable for models testing Hypothesis 2 will be group and we will include all four time points. Since participants were randomly assigned to group, this test allows for the highest internal validity in terms of causal conclusions about the effects of THC. If, on the other hand, participants titrate their own use such that there are few reliable between-groups differences, then actual blood levels of THC will become the between-groups (continuous) independent variable in tests of Hypothesis 2 and we will utilize timepoints 3-4 as the within-subjects effect of time. Our preliminary studies confirm wide variability in THC levels even among individuals using the same strain, so there will be adequate between-participant variability for these analyses. In either case, we will again use the RCR approach described above, and standard approaches to the estimation of interactions in regression (Aiken & West, 1991) in the case of a continuous IV (i.e., mean-centering prior to creation of the interaction term). In each model, the predictors will include the group variable (or continuous THC blood levels), a time variable, and their interaction.

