**Appointment 1, Baseline Assessment Procedure (Session 1).** Subjects who meet inclusion criteria will be scheduled for the first available appointment, baseline session. After arriving at the lab, subjects will be provided with a consent form. Each subject will be breathalyzed to insure that they have not been drinking alcohol prior to each appointment. A urine toxicology screen will also be administered to insure that subjects have not recently use illicit drugs other than cannabis. Additionally, female participants will be required to take a urine pregnancy test (provided by the study team at no cost to the participant). A member of our research team who has completed a certified training in phlebotomy will collect a blood sample. All blood draw procedures performed during this study will involve collecting venous blood via venipuncture of a peripheral arm vein using standard, sterile phlebotomy techniques. Subjects will then complete measures related to alcohol and drug use, cannabis withdrawal, cannabis craving, measures of mood, and neurocognitive measures (see section below for details of measures to be completed). After completing the measures, each participant will be scheduled for their 2nd appointment to include Sessions 2, 3, & 4. Before the participant leaves this appointment they will be given instructions to purchase 3 grams of either a normally high THC strain, a medium THC strain, or a low THC strain at a dispensary (The Farm) in Boulder, Colorado to be used for 5 days as they normally would, they will also be given a gut microbiome collection kit to take home with them and bring back at their 2nd appointment.

**Appointment 2, Mobile Lab Experimental Procedure (Session 2, 3, 4).** For Sessions 2, 3 & 4 the study coordinator will drive the mobile lab to a location close to the participant's home. The participant will come to the mobile lab where they will complete a blood draw (22 ml), self-report measures, and the cognitive tests for Session 2. At the end of Session 2, participants will return to their home to use the assigned strain as they normally would.

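### The amount and time of the home use that produces the Session 3 and 4 blood values are not recorded, so titration is inferred only from blood THC levels that fail to differ

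*Protocol*

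**What the plan says.** **Hypotheses.** Protocol section I (Hypothesis 1) expects higher blood THC with higher-THC strains. As the alternative, it says that users may titrate by potency and reach the same blood levels.

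**Dose.** The section on the rationale for the administration procedure concedes little control over how, or how much, participants use. It answers that "regardless of how the participant uses the marijuana, we have an objective measure of the dose received for both THC and CBD".

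**The episode that matters.** Section XII: "At the end of Session 2, participants will return to their home to use the assigned strain as they normally would". They then return for the Session 3 draw, and Session 4 follows.

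**Amount data that do exist.** Under administration at home, participants are prompted during the five days to "report how much was used each day using an online reporting system". The instrument table in section XII also lists a timeline follow-back with amount per day at Sessions 1 and 2. Its stated window is the 30 days before baseline.

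**How titration is recognised.** In the section on effects of THC potency, the Hypothesis 2 text moves from randomised group to observed blood THC as predictor if "participants titrate their own use such that there are few reliable between-groups differences". The same section reports wide variation in blood THC among people using the same strain.

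**The concern.** Titration is a statement about behaviour: less product taken when it is stronger. The plan recognises it only by its presumed result, blood levels that do not differ. Blood THC reflects amount, potency, inhalation and time since use together. Similar group levels can therefore arise from titration, or from equal amounts with large person-to-person variation and limited precision.

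The error can also run the other way. The protocol's background describes users who smoked less of the stronger product and still became more intoxicated. Partial titration of that kind would leave a blood difference, and the plan would not detect it.

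At stake is the interpretation of one of the two stated outcomes of Hypothesis 1. A null blood result could be reported as evidence that users compensate for potency when no measure of amount supports that.

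**Working it through.** **1. What is recorded, and when**

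| Period | Amount used | Time of use |
|---|---|---|
| 30 days before baseline | timeline follow-back, self-report | by day |
| Five home days | daily online self-report | by day |
| Home use between Sessions 2 and 3 | none listed | none listed |

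The Session 3 and 4 instruments are the drug-effects and ARCI scales, exercise cognitions, cold pressor, blind guess, heart rate, cognition, craving, mood and blood. The compliance check covers receipt and label, not quantity. A day-five online report might include the session use, but the protocol does not say so or separate it. The design overview sets Session 4 at 60 minutes after last use, while section XII sets it at one hour after Session 3. Neither says that the time of last use is written down.

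**2. The plan's own sample size**

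Inputs from the power section: "with three groups, four assessment points, and an average ICC = .6 between assessment points", f = .12, N = 99, two-tailed alpha .05.

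- Noncentrality = f²·N·m/(1 − ρ) = 0.0144 × 99 × 4 / 0.4 = 14.26, with 6 and 288 df.
- Power (sphericity assumed) = 0.811. Allowing for 10% attrition, 33/0.9 = 36.7, so 37 per group and 111 in total.

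The stated figures reproduce, and this point does not depend on them. They describe the chance of detecting an interaction. They do not make a non-significant result evidence of equality.

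**3. What a missing blood difference can show**

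Pairwise contrast at one time point, n = 33 per group, power ≈ Φ(d·√(n/2) − 1.96):

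| d | 0.3 | 0.5 | 0.6 | 0.7 |
|---|---|---|---|---|
| power | 0.23 | 0.53 | 0.68 | 0.81 |

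The protocol gives no SD for blood THC. Assume a log-scale SD s of 0.5 to 1.25. The 95% interval for a ratio of two strains then extends by a factor exp(1.96·s·√(2/33)), which is 1.27 to 1.83 each way. Power for a true 1.5-fold difference falls from 0.91 to 0.26 over that range.

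**4. What a direct test of amount could show**

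Full titration over 6%, 12% and 18% flower predicts amounts in the ratio 3 : 1.5 : 1. The logs of 6, 12 and 18 are 1.792, 2.485 and 2.890, with mean 2.389. The root mean square deviation is √[(0.597² + 0.096² + 0.501²)/3] = 0.454. Then f = 0.454/SD for full titration and half that for half titration. A three-group one-way ANOVA has noncentrality N·f². With N = 99:

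| Assumed SD of log amount | 0.6 | 0.8 | 1.0 |
|---|---|---|---|
| Full: f | 0.76 | 0.57 | 0.45 |
| Full: power | 1.00 | 0.999 | 0.984 |
| Half: f | 0.38 | 0.28 | 0.23 |
| Half: power | 0.92 | 0.70 | 0.50 |

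**5. Fewer flower users**

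Only flower strains are randomised. Edible users form naturally occurring groups, and the flower/edible split of the 99 is not clear. If 66 or 48 were flower users (assumed), half-titration power at SD 0.8 falls from 0.70 to 0.51 or 0.38.

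**The case against.** Several counter-arguments carry weight.

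- **Amount is measured.** A reader might infer that consumption before Session 3 is never recorded. The documents do not support that: daily amounts are reported for the five home days, and a timeline follow-back is listed. Only the session episode lacks a measure. That gap stands, because an analysis plan cannot recover data that were not collected.
- **Analysing the daily amounts may belong to the SAP.** This is fair, and the absence of such an analysis is not a fault in itself. What the protocol does fix is reading titration from blood levels.
- **Delay to the draw.** A reader might infer that varying delays would equalise the arms. The mobile lab was adopted to remove a 10 to 20 minute delay, with blood drawn on arrival. In blinded, randomised flower arms, any remaining delay unrelated to strain adds noise and does not bias the arms toward each other.
- **The Hypothesis 2 switch.** A reader might infer that the switch is invalid without amount data. It turns on whether blood levels differ, not on why, so weighing product would not alter it.
- **The wording is hedged.** Titration is offered as a possibility, and amount used is not a named outcome. This lowers the severity. But titration is the stated alternative to Hypothesis 1, and nothing in the stated plan tests it directly.
- **Lower amount is not the only form of titration.** The background cites fewer puffs and smaller inhalation volumes at higher potency. Equal weight used therefore does not rule titration out, and the fix must say so.

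**Conclusion.** The point holds in a limited form. The amount and time of the home use behind the Time 3 and Time 4 blood values are not recorded. Blood THC is called the dose received although it is an exposure measure and the Hypothesis 1 outcome. Titration is inferred only from few between-group blood differences, which the design cannot turn into evidence of equality: power is about 0.53 for a pairwise d of 0.5 at one time point.

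A direct comparison of amounts would be close to decisive for full titration if all 99 were flower users. For half titration it would be only moderate, from 0.92 down to 0.50, and lower with fewer flower users. Every SD here is an assumption, because the protocol gives none. The sample size is not in error. This is a worthwhile, inexpensive improvement and does not invalidate the trial.

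**What to change.** 1. In flower participants, analyse the daily amounts already collected by randomised strain: log amount, and amount × certified potency derived after unblinding. Name this as the direct test of titration.
2. For the use between Sessions 2 and 3, record the time of last use and the amount. For flower, this can be bottle weight before and after, taken by participant or staff, or a self-report item. For edibles, use a unit count.
3. Describe blood THC as exposure, not as dose received.
4. Do not report titration from a null blood difference alone. Support it with lower amount used at higher potency. Otherwise report the result as inconclusive, and note that titration by inhalation at equal weight cannot be excluded.
5. Leave the rule for choosing the Hypothesis 2 predictor as it is.

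**Cost.** Item 1 needs one added model and no new data. Item 2 adds a short entry or two weighings per participant. Staff weighing would be a new procedure in a study whose logistics followed legal advice, so participant weighing or self-report may be easier. The protocol also does not say that participants bring the bottle, only that staff see its label. Weights cannot separate product used from product shared or spilled.

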### **Assessment of Compliance.**

We ask participants to bring the receipt from the dispensary to verify which strain was purchased, and the RA visually confirms the label (e.g., A, B, or C) at the experimental session.

### **Mobile Laboratory Experimental Session.**

A member of our research team who has completed a certified training in phlebotomy will collect blood samples from participants (see preliminary studies above for cannabinoid blood level data). All blood draw procedures performed during this study will involve collecting venous blood through venipuncture of a peripheral arm vein using standard, sterile phlebotomy techniques. The amount of blood to be drawn will vary for each appointment. We will collect 32 ml of blood during Appointment 1 (Baseline/Session 1). We will use 10 ml of that blood for DNA extraction, 20 ml of blood to perform the inflammatory analysis, and 2 ml of blood for cannabinoid analysis. During Appointment 2 (Sessions 2-4), we will collect 22 ml of blood (20 ml for inflammatory analysis and 2 ml for cannabinoid analysis). The 2 ml of blood will be used to examine changes in levels of cannabinoids (i.e., THC, CBD) from pre- to post-five days of use of the randomly assigned strain.

### **Laboratory Post-Experimental Appointment.**

#### **DNA Collection.**

DNA will be extracted from the 10 ml of blood collected during Appointment 1. After extraction, DNA will be quantified and stored at  $-80^{\circ}$  for future analysis. DNA will be collected only at Appointment 1 in order to look at differences in single nucleotide polymorphisms (SNPs) in heavy cannabis users versus light cannabis users. The DNA samples collected in this study are for biobanking purposes only. Analysis of these samples are expected to be performed at a future date and therefore will not contribute to the current study at this time.

**Blood levels of cytokines.** Two tubes of blood (20 ml) will be drawn at Appointments 1 & 2 and used to observe changes in inflammatory markers. Blood samples will be assayed for IFN $\gamma$ , IL-1a, IL-1b, IL-6, IL-2, IL-4, IL-8, IL-10, IL-12, and TNF. This is the same assay used in our preliminary studies. The blood samples will be used to examine changes in inflammatory markers (i.e., THC, CBD) from pre- to post-five days of use of the randomly assigned strain.

**Lipopolysaccharide (LPS)-PBMC challenge.** We also expect different strains cannabis, with their varying cannabinoid content, to impact the responses of blood monocyte cells to an LPS challenge. LPS stimulation of PBMCs simulates the TLR4 inflammation cascade. Cannabis has been shown to mediate the pro-inflammatory effects of LPS. Peripheral blood mononuclear cells (PBMC) will be separated using density gradient centrifugation. Cells will be counted and viability assessed using trypan blue exclusion. PBMCs will be exposed to LPS (0, 0.1, 1, 10 and 100 ng/ml) for 20h in a 96 well v-bottom plate. Protein levels of cytokines and chemokines (IL1, TNF, IL6, IL4, IL10, IFN $\gamma$ , MIP-1a) will be measured in supernatant using a multiplex ELISA assay (Aushon Biosystems, Billerica MA). mRNA levels of the same cytokines and chemokines will be measured in cell lysates using real-time PCR. We have successfully performed the PMBC isolation and LPS challenge in other projects.

**Gut Microbiome Sample Collection.** We expect to see changes in both the number and diversity of microbiota populations found in the gut as a result of cannabis use. Because inflammation and the gut microbiome are heavily intertwined, we will examine the relationship between changes in the gut microbiome with changes in inflammatory biomarkers in the blood (cytokines and blood monocyte cell response to LPS challenge) as a result of cannabis use. Fecal samples will be collected from participants using at-home kits and then stored at  $-80^{\circ}$ . Microbial DNA will be extracted from fecal samples and then analyzed to determine how many and which bacterial species are present in the gut. Gut microbiome data will be collected at two time-points during this study. Subjects will be given the at-home collection kits at their 1st appointment and will

return them to a research assistant at their 2nd appointment. The microbial DNA collected in this study are for biobanking purposes only. Analysis of these samples are expected to be performed at a future date and therefore will not contribute to the current study at this time.

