**Criteria for inclusion in the study are:**

1. Must be between the ages of 21 and 70 and provide informed consent;
2. Must have prior experience with edibles in order to be eligible to participate in the edible group;
3. Must have used marijuana at least 4x per month in the past month. This includes any form of marijuana consumption including flower, oil, wax, tinctures and edibles;

4. Must not report currently using a strain with greater than 1% CBD or less than 18% THC. This will ensure that there are no subjects who could be harmed by switching to a lower CBD/higher THC strain. All of the subjects in our preliminary study would have met this criterion.
5. Must not be a University of Colorado student or employee;
6. Must report not using other drugs (cocaine, opiates, methamphetamine) in the past 60 days or test positive on a urine test for those drugs of abuse at baseline;
7. Must not smoke greater than 5 cigarettes a day;
8. Must have a breath alcohol level of 0 at screening (to sign consent form) and must not report drinking greater than 3x per week and greater than 5 drinks on occasion for men and 4 drinks on occasion for women;
9. Female subjects must not be pregnant, as indicated by a pregnancy test which will be administered at baseline, or trying to become pregnant;
10. Must not donate plasma, blood, or platelets for 7 days prior to the 2 appointments and 7 days after;
11. Must not be in treatment for psychotic disorder, bipolar disorder or schizophrenia.

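### The five-day change in inflammatory markers and the microbiome is attributed to cannabis use, but every participant is already a regular user at the first sample, so the design can show at most an effect of assigned THC potency

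*Protocol*

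**What the plan says.** Three parts of Protocol section IV bear on this.

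- **Blood levels of cytokines.** Blood from Appointments 1 and 2 is to be used to examine "changes in inflammatory markers (i.e., THC, CBD) from pre- to post-five days of use of the randomly assigned strain". The parenthesis names cannabinoids rather than cytokines, evidently a slip. The paragraph names no comparison between strains.
- **LPS-PBMC challenge.** Here the expectation is about strains: "We also expect different strains cannabis, with their varying cannabinoid content, to impact the responses of blood monocyte cells to an LPS challenge".
- **Gut Microbiome Sample Collection.** The opening sentence is causal: "We expect to see changes in both the number and diversity of microbiota populations found in the gut as a result of cannabis use". The next links microbiome change to "changes in inflammatory biomarkers in the blood (cytokines and blood monocyte cell response to LPS challenge) as a result of cannabis use". The paragraph ends by placing the microbial DNA in a biobank for later analysis outside the current study.

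Section VI (inclusion criteria) fixes who is sampled. Criterion 3 reads "Must have used marijuana at least 4x per month in the past month", and criterion 4 reads "Must not report currently using a strain with greater than 1% CBD or less than 18% THC".

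For flower users, the choice of strain "will be urn randomized across participants such that equal numbers of male and female participants are included in the high, medium, and low conditions" (Marijuana Administration at Home). Edible users are not assigned a product. They keep to their usual use and fall into low, medium and high groups by their own choice (Overview and Design of Study 1).

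**The concern.** The wording names an effect of cannabis use. To estimate it, some people would have to be unexposed, or exposure would have to start or stop between the two samples. Neither happens. The first sample comes from regular users, and every arm goes on using cannabis for the next five days. A change common to all participants could reflect lower potency, time, the move from the laboratory to the mobile van, or regression to the mean. The data cannot separate these.

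What is at stake is interpretation. The protocol's significance section intends the results to inform the public and policy makers. A shift in cytokines, or later in gut flora, reported as a consequence of cannabis use would be a claim that the study cannot support at any sample size.

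**Working it through.** The question is what each available contrast estimates. The protocol gives no sample-size figure for these markers.

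**1. Planned exposure change, flower users.** Inputs: usual potency about 18% THC (Objectives; Overview and Design of Study 1) and assigned potencies of 18%, 12% and 6% (Marijuana Administration at Home).

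| Arm | Usual to assigned | Change in percentage points |
|---|---|---|
| High | 18 to 18 | 0 |
| Medium | 18 to 12 | -6 |
| Low | 18 to 6 | -12 |

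Mean change with equal arms: (0 - 6 - 12)/3 = -6 points.

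Criterion 4 excludes anyone reporting a strain below 18% THC. If a participant's usual potency is h, with h at least 18, the changes are 18 - h, 12 - h and 6 - h. None is positive. The differences between arms stay at 6 and 12 points whatever h is. The pooled change is thus a reduction in potency mixed with time effects, while the between-arm difference is a clean potency contrast. It is potency as assigned: participants choose how much to use, so the dose received is not fixed.

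**2. Each contrast and what it identifies.**

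| Contrast | What it identifies |
|---|---|
| Pooled or within-arm change, Session 1 to Session 2 | No causal effect; there is no unexposed or concurrent comparator |
| Session 2 across randomised flower arms, given Session 1 | Effect of assigned THC potency |
| Edible groups, any comparison | Association only; groups are self-selected and exposure is not changed by the study |
| Session 2 (sober) to Sessions 3 and 4, blood only | Acute within-person change, uncontrolled for time |

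No row gives use against non-use over the five days. The acute contrast in the last row is a different question and does not apply to stool.

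**3. Covariate against change score.** Take equal variances at the two sessions and correlation r.

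- Error variance of a change score: 2(1 - r).
- Error variance with baseline as covariate: 1 - r².
- Ratio: (1 - r²) / [2(1 - r)] = (1 + r)/2.

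The protocol gives no r for inflammatory markers. Borrowing .6 from its power section, which concerns other outcomes, the ratio is 1.6/2 = .80. At r = .4 it is .70, and at r = .8 it is .90.

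**4. What the strain contrast could detect (illustration).** Assume 33 flower participants per arm, two-sided alpha .05, power .80 and a normal approximation. The detectable pairwise difference is (1.960 + 0.842) × √(2/33) × SD = 2.802 × 0.246 × SD.

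- Change score at r = .6: SD = √0.8 = 0.894, giving 0.62 baseline SDs (0.76 at r = .4, 0.44 at r = .8).
- Baseline as covariate at r = .6: SD = √(1 - .36) = 0.80, giving 0.55 baseline SDs.

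The defensible comparison can therefore detect only fairly large potency effects on any one marker.

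**The case against.** The strongest reply is that this is loose wording in a specimen-collection section. The main quoted clause comes from a sentence about the association between two sets of changes, and that sentence needs microbiome data whose analysis is deferred. The LPS paragraph already speaks of differences between strains. The detailed model for secondary markers may properly sit in an analysis plan that is not shown. All of this stands, and it limits the weight of the point. It does not remove it: the protocol names a causal effect that its own eligibility criteria rule out, and an analysis plan cannot supply the missing comparator.

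Two stronger readings are tempting, and neither is supported.

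- **A reader might infer that the protocol commits to a pooled, uncorrected before-after test on each cytokine, leaving the randomisation unused.** It states no such test, no pooling and no alpha for these markers. The same phrase, "from pre- to post-five days of use of the randomly assigned strain", is used for blood cannabinoids under Mobile Laboratory Experimental Session, and blood THC is analysed as strain by time in the analysis of Hypothesis 1. No false-positive rate can be attached to a test that the protocol does not state.
- **A reader might infer that the between-strain comparison would show the effect of cannabis use.** It would not. It shows the effect of assigned potency among continuing users, and is randomised for flower only.

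It is also fair to say that analysing change scores by strain would be valid. The covariate form is simply more precise.

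**Conclusion.** The point holds and is minor. The five-day change cannot show that cannabis use alters inflammatory markers or the microbiome, because every participant is a regular user at the first sample and no arm stops. This follows from the eligibility criteria and the design, and depends on no numerical assumption. The potency changes of 0, -6 and -12 points rest on a usual potency of about 18%; if it is higher, every arm moves further down and the between-arm gaps are unchanged. The precision gain of 20% (30% to 10%) rests on an assumed correlation of .6 (.4 to .8). The markers are not outcomes of Hypotheses 1 or 2, so the main conclusions of the study are not affected.

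**What to change.** In the cytokine and LPS paragraphs, state that:

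- among randomised flower participants, Session 2 values are compared across the three assigned strains with the Session 1 value as covariate;
- pooled or within-arm pre-post change is descriptive;
- all results in edible users are descriptive;
- any change from Session 2 to Sessions 3 and 4 in blood markers is a separate acute within-person contrast, uncontrolled for time.

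In the microbiome paragraph, replace the attribution to cannabis use with 'by assigned THC strain', so that it also governs the deferred analysis. That paragraph should also say when the first stool sample is taken. Kits are handed out at Appointment 1 and returned at Appointment 2, so the text does not ensure that the first sample precedes use of the assigned strain.

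The cost is protocol wording, with no new participants or blood samples. The downside is that the study no longer claims an inflammatory or microbiome effect of cannabis use itself.
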